12.6.2 Primary Analysis Methods

The neutralizing antibody titers to the SARS-CoV-2 index virus will be collected and quantified as described in Section 10. As all subjects are previously vaccinated, it is not expected that a large number of titer values will be below the limits of quantitation or detection. In the case a titer result is below the limit of detection, a value of half the limit of detection will be used for analysis purposes. In the event a titer value is at least the limit of detection but below the limit of quantitation, a value of half the limit of quantitation will be used for analysis purposes.

A generalized linear model will be used to compare the SARS-CoV-2 neutralizing antibody titers (on the log₁₀ scale) at 2 weeks after trial vaccination between the vaccination groups with age and baseline titers included as covariates. The least squares means and the corresponding 97.5% CI from the model will be back transformed to their original scale via exponentiation for ease of interpretation.

If the non-inferiority success criterion is met (lower bound of the 97.5% CI is \geq 0.67), the p-value from the same model will be reported to assess superiority.

12.6.3 Sensitivity and Supportive Analyses

The primary analysis will be supported by descriptive summaries (GMT, their 95% CIs and the median) for each time point (pre- and post-vaccination). Besides summarizing data by cohort, summaries and the 95% CI will also be presented for combined Part A Cohorts 1 and 2.

The proportion of subjects with \geq 2-fold and \geq 4-fold increase in neutralizing antibody titers to the SARS-CoV-2 index virus from baseline to 2 weeks after trial vaccination will be summarized using frequencies and percentages within cohort and arm.

ABNCoV2		Clinical Trial Protocol
ABNCoV2-03	Edition 8.0	

Nucleocapsid protein test results will be used to perform additional sensitivity analyses of the primary endpoint. Test results that are indicative of SARS-CoV-2 infection will be used to exclude subjects from the analysis population as potential additional subjects experiencing the intercurrent event of COVID-19 infection prior to the 2 week timepoint.

Since the window between vaccination and the primary endpoint measurement is short, the number of subjects with missing data is expected to be small. If there are any, missing data will be imputed using a multiple imputation method as a sensitivity analysis for subjects who meet the Safety Analysis Set definition.

12.6.4 Subgroup Analyses

The primary analysis will also be repeated for the following subgroups: prior vaccination regimen (per randomization strata in Section 12.1), age (<65 years and \geq 65 years), baseline neutralizing titer to SARS-CoV-2 index virus (<Limit of Quantification, <median of all subjects in Part A, \geq median of all subjects in Part A), time from previous vaccination, history of SARS-CoV-2 infection and baseline comorbidity. If the number of subjects with known history of SARS-CoV-2 infection is small, the analysis for this subgroup will only be performed for subjects without known history of SARS-CoV-2 infection.

12.7 Secondary Analyses

12.7.1 Secondary Estimand

The key secondary variables of interest are the subjects' neutralizing antibody titers against circulating SARS-CoV-2 VOCs measured at 2 weeks after trial vaccination in Part A, and they will be summarized as the ratios of GMTs for ABNCoV2 compared to Comirnaty.

The null hypothesis of inferiority will be rejected if the ratio of GMTs against the SARS-CoV-2 VOCs, for ABNCoV2 vaccine compared to Comirnaty vaccine, is within the non-inferiority margin of 0.67. Only Part A cohort(s) that meet the primary success criterion will be formally tested sequentially for non-inferiority of ABNCoV2 to Comirnaty for each VOC, and a Bonferroni correction will be used to control the overall type I error rate for the trial. Details are provided in Section 12.3.

The intercurrent events for the secondary analyses are the same as for the primary analysis and will be handled in a similar fashion (Section 12.6.1).

Besides the key secondary variables of interest, other secondary variables include the subjects' neutralizing antibody titers against the SARS-CoV-2 index virus measured at 2 weeks after ABNCoV2 vaccination in the immunogenicity subsets of Part B Cohort 1 and Cohort 2. These will be summarized descriptively using GMTs, 95% CIs, and medians.

ABNCoV2		Clinical Trial Protocol
ABNCoV2-03	Edition 8.0	

12.7.2 Secondary Analysis Methods

The VOCs for Part A will be analyzed using the same analysis methods as those for the primary estimand described in Section 12.6.2. The precision of the CIs will be adjusted based on the number VOCs included in the key secondary analyses. The decision regarding which VOCs to include will be finalized before sample analysis begins. The GMT ratios, adjusted CIs for the non-inferiority hypothesis testing, as well as 95% CIs will also be calculated as descriptive information.

If the non-inferiority success criterion is met for a VOC (lower bound of the 97.5% CI is \geq 0.67), the p-value from the same model will be reported to assess superiority.

Analyses of other VOCs may also be performed similarly but not subjected to formal testing; such comparisons thus will not affect the trial-wide type I error.

Analyses of Part B Cohort 1 and Cohort 2 will consist of descriptive summaries (GMTs, 95% CIs, and medians) for each time point (pre- and post-vaccination).

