Success Criterion for Key Secondary Endpoint	If both Cohort 1 and Cohort 2 are tested for and meet the success criterion for the primary endpoint, VOCs will be tested in the cohort with the higher number of evaluable subjects, followed by the cohort with the smaller number of evaluable subjects if the success criterion is met in at least one of the tested VOCs in the cohort tested first. In the event only one cohort meets the success criterion for the primary endpoint, VOCs will be formally tested for the successful cohort only. Ratios of GMTs for the VOCs at 2 weeks after trial vaccination, for ABNCoV2 vaccine compared to Comirnaty vaccine, will be tested using the non-inferiority margin of 0.67 as was used for the primary endpoint. The result will be based on the lower limit of a two-sided CI with coverage determined based on the number of VOCs circulating at the time of the trial. A Bonferroni correction will be employed for the simultaneous non-inferiority tests to control the trial-wide type I error.	
	If the non-inferiority criterion is met, a superiority test will be carried out based on the same type I level.	
	If the non-inferiority criterion is met in at least one cohort and one VOC, supportive analyses will include assessing non-inferiority or superiority in Cohort 1 and Cohort 2 combined.	
Other Secondary Endpoint Population- level Summary	Part B: GMTs of neutralizing antibodies against the SARS-CoV-2 index virus at 2 weeks after trial vaccination in subjects receiving ABNCoV2 in the immunogenicity subsets of Part B Cohort 1 and Cohort 2.	
Safety Endpoint Population-level Summaries	 Part A: For all subjects receiving ABNCoV2 compared to those receiving Comirnaty, the percent who report the safety endpoints listed below. Parts A and B: For all subjects receiving ABNCoV2, the percent who report the safety endpoints listed below. 	
	Safety endpoints:	

3

ABNCoV2		Clinical Trial Protocol
ABNCoV2-03	Edition 8.0	

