12.3 Multiplicity

The hypothesis test of noninferiority of ABNCoV2 to Comirnaty in terms of neutralizing antibody titers for SARS-CoV-2 will be performed in Part A in up to 2 cohorts. A Bonferroni correction will be used to control the trial-wide type I error of $\alpha = 0.025$, one-sided. In the event a cohort does not meet the requirement of 400 evaluable subjects for the primary endpoint analysis, summaries for the under-enrolled cohort will be considered purely descriptive.

ABNCoV2-03

The key secondary endpoints, ratios of GMTs for the VOCs at 2 weeks after trial vaccination, will be formally tested in Part A for non-inferiority of ABNCoV2 to Comirnaty only in the cohort(s) in which the primary success criterion is met. If the primary success criterion is met in only one cohort, VOCs will be formally tested in that cohort only. A Bonferroni adjustment will be used such that each VOC non-inferiority hypothesis will be tested at the α =

 $\frac{0.025}{number of VOCs tested}$ level. For example, if 3 VOCs are tested, each test will be performed at the α = 0.0083 level such that success would require the lower confidence limit of a 98.3% CI to be at least 0.67. In the event that success criteria are met for both Cohort 1 and Cohort 2, the number of tests will multiply, and thus non-inferiority hypothesis will be tested at the α =

 $\frac{0.0125}{number of VOCs tested}$ level so that the overall type I error rate will be no more than 5%.

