### 2.1. Multiplicity Adjustment

The hypothesis test of non-inferiority of ABNCoV2 to Comirnaty in terms of neutralizing antibody titers for SARS-CoV-2 will be performed in Part A in up to 2 cohorts. A Bonferroni correction will be used to control the trial-wide type I error of  $\alpha = 0.025$ , one-sided. In the event a cohort does not meet the requirement of 400 evaluable subjects for the primary endpoint analysis, summaries for the under-enrolled cohort will be considered purely descriptive.

The key secondary endpoints, ratios of GMTs for the VOCs at 2 weeks after trial vaccination, will be formally tested in Part A for non-inferiority of ABNCoV2 to Comirnaty only in the cohort(s) in which the primary success criterion is met. If the primary success criterion is met in only one cohort, VOCs will be formally tested in that cohort only. A Bonferroni adjustment will be used such that each VOC non-inferiority hypothesis will be tested at the  $\alpha =$

$\frac{0.025}{\text{number of VOCs tested}}$  level. For example, if 3 VOCs are tested, each test will be performed at the

$\alpha = 0.0083$  level such that success would require the lower bound of a 98.3% CI to be at least 0.67. In the event that success criteria are met for both Cohort 1 and Cohort 2, the number of tests will multiply, and thus non-inferiority hypothesis will be tested at the  $\alpha =$

$\frac{0.0125}{\text{number of VOCs tested}}$  level so that the overall type I error rate will be no more than 5%.

Due to the challenges of finding non-boosted potential trial subjects during enrollment, Cohort 1 was under-enrolled for the primary analysis, even with extension of the enrollment period. Therefore, only Cohort 2 will be formally tested.

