##### **4.3.1.2. Main Analytical Approach**

The VOCs for Part A will be analyzed using the same analysis methods as those for the primary estimand described above. The precision of the CIs will be adjusted based on the number VOCs included in the key secondary analyses. The decision regarding which VOCs to include will be finalized before sample analysis begins. The GMT ratios and CIs with coverage adjusted for the non-inferiority hypothesis testing will also be calculated.

If the non-inferiority success criterion is met for a VOC (lower bound of the adjusted CI is  $\geq 0.67$ ), the p-value from the same model will be reported to assess superiority.

Analyses of other VOCs may also be performed similarly but not subjected to formal testing; such comparisons thus will not affect the trial-wide type I error.

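### Protocol 12.7.2 fixes the VOC non-inferiority criterion at a 97.5% CI, while every other statement of the rule sets coverage by the number of VOCs; with one cohort tested, the two agree only for two VOCs

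*Protocol*

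**What the plan says.** Protocol 12.7.2 says two different things. Its first paragraph states: "The precision of the CIs will be adjusted based on the number VOCs included in the key secondary analyses". Its second paragraph then gives the criterion that opens the superiority step: "If the non-inferiority success criterion is met for a VOC (lower bound of the 97.5% CI is" at least 0.67, with no dependence on the number of VOCs.

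The other places that set the VOC rule agree with the first paragraph:

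- Protocol 1.3 (synopsis, key secondary success criterion) bases the result on the "lower limit of a two-sided CI with coverage determined based on the number of VOCs circulating at the time of the trial".
- Protocol 12.3 sets one-sided alpha at 0.025 divided by the number of VOCs when one cohort succeeds. For three VOCs, "success would require the lower confidence limit of a 98.3% CI to be at least 0.67".
- Protocol 12.7.1 states that "a Bonferroni correction will be used to control the overall type I error rate for the trial. Details are provided in Section 12.3".
- SAP 2.1 repeats the rule and the example: "success would require the lower bound of a 98.3% CI to be at least 0.67". It adds that Cohort 1 was under-enrolled and only Cohort 2 will be formally tested.
- SAP 4.3.1.2 has nearly the same sentence as Protocol 12.7.2, but with different coverage: "If the non-inferiority success criterion is met for a VOC (lower bound of the adjusted CI is" at least 0.67.

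Protocol 12.6.2 has the matching sentence for the index virus: "If the non-inferiority success criterion is met (lower bound of the 97.5% CI is" at least 0.67. There the 97.5% CI is correct, because the primary test runs at one-sided 0.0125 per cohort.

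**The concern.** VOC non-inferiority is the key secondary claim, and 12.7.2 is the protocol section that describes its analysis. Read literally, its criterion and the rule in 12.3 can give one VOC result opposite verdicts: a pass under 12.7.2 and a fail under 12.3 when k is 3 or more, and the reverse when k is 1.

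The dates do not settle which text governs. SAP 1.0 is dated 19 May 2023 and is based on protocol Edition 7. Protocol Edition 8.0 is dated 30 June 2023 and still reads 97.5%. The SAP introduction says departures from the protocol are described in SAP 4.8, but that section does not mention this difference.

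**Working it through.** **Inputs.** One-sided alpha per VOC of 0.025/k with one successful cohort (Protocol 12.3, SAP 2.1). Margin 0.67, SD 0.52 on the log10 scale, 1:1 allocation, 450 evaluable, minimum 400 (Protocol 12.2.1, SAP 5.1). The value of k is not given in the documents; k from 1 to 5 is shown.

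**1. The plan's own figures.** For k=3, 0.025/3 = 0.00833 and 1 - 2 x 0.00833 = 98.33%, matching the stated 0.0083 and 98.3%. Primary power at one-sided 0.0125 and true ratio 1, by normal approximation, is 0.904 at 450 evaluable (stated: about 90%) and 0.865 at 400 (stated: about 86%). Both reproduce.

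**2. Required coverage and the family bound of the literal text.** Required two-sided coverage is 1 - 2 x 0.025/k. If every VOC is tested with a 97.5% CI, the Bonferroni bound on the family error is k x 0.0125.

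| k | coverage under 12.3 | literal 12.7.2 | family bound, literal text | bound under 12.3 |
|---|---|---|---|---|
| 1 | 95% | 97.5% | 0.0125 | 0.025 |
| 2 | 97.5% | 97.5% | 0.025 | 0.025 |
| 3 | 98.33% | 97.5% | 0.0375 | 0.025 |
| 4 | 98.75% | 97.5% | 0.05 | 0.025 |
| 5 | 99% | 97.5% | 0.0625 | 0.025 |

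These are upper bounds. If the VOC tests were independent, the literal text would give 1 - (1 - 0.0125)^k = 0.037, 0.049 and 0.061 for k=3, 4 and 5. VOC titers in the same serum are likely to be positively correlated, which lowers these figures. With an assumed equal correlation of 0.8, the error is 0.026 for k=3 and 0.034 for k=5.

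**3. Smallest observed ratio that passes.** Threshold = 10^(log10(0.67) + t(1 - alpha, N - 2) x SE), with SE = 0.52 x sqrt(2/n) and n per arm. For 450 evaluable, SE = 0.52 x sqrt(2/225) = 0.0490. This assumes that the SD used to size the index-virus test also holds for VOCs, and that the age and baseline-titer covariates bring no gain.

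| | literal 97.5% | k=1 | k=2 | k=3 | k=4 | k=5 |
|---|---|---|---|---|---|---|
| 450 evaluable | 0.864 | 0.836 | 0.864 | 0.879 | 0.889 | 0.897 |
| 400 evaluable | 0.877 | 0.848 | 0.877 | 0.894 | 0.905 | 0.913 |

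**4. How often the verdict on one VOC would differ.** Pass probabilities from the noncentral t distribution, 225 per arm, same assumptions:

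| one-sided alpha | true ratio 1 | true ratio 0.9 |
|---|---|---|
| 0.0125 (literal) | 0.903 | 0.643 |
| 0.025 (k=1) | 0.943 | 0.742 |
| 0.025/3 (k=3) | 0.873 | 0.584 |
| 0.005 (k=5) | 0.831 | 0.512 |

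The differences from the first row give disagreement of about 4% and 10% for k=1, 3% and 6% for k=3, and 7% and 13% for k=5, at true ratios 1 and 0.9.

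**The case against.** The strongest reply is that one parenthesis is out of line and everything else is consistent. The synopsis, Protocol 12.3, Protocol 12.7.1 by cross-reference, SAP 2.1 and SAP 4.3.1.2 all carry the adjusted rule, and 12.7.2 itself calls for adjusted CIs one paragraph earlier. The 97.5% is probably carried over from 12.6.2. Edition 8.0 was issued for the nucleocapsid analyses, so its later date does not show that the sponsor chose a fixed 97.5%. All of this stands, and it makes a wrong analysis unlikely.

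It is also true that the sentence triggers only the reporting of the superiority p-value. At 450 evaluable and SD 0.52, superiority needs an observed ratio of about 1.25 (one-sided 0.025) to 1.34 (0.005). Every non-inferiority threshold in question lies between 0.84 and 0.90, so the choice of coverage cannot change a superiority conclusion.

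The size in ratio terms is conditional. The SD of 0.52 was chosen for the index virus, the documents give no VOC figure, and covariate adjustment could make the intervals narrower and disagreement rarer.

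What remains is that the sentence states a non-inferiority success criterion, and the stated coverage is wrong for every k except 2.

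**Conclusion.** The text is wrong as written and should be corrected. With Cohort 2 alone tested, the 97.5% CI meets the plan's own rule only for k=2. For k=3 and k=5 it allows a family bound of 0.0375 and 0.0625 against 0.025; for k=1 it is stricter than needed. The coverage mismatch follows from the documents alone. The ratio thresholds and disagreement rates rest on SD 0.52 for VOCs, no covariate gain, and a k that the documents leave open.

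Three stronger readings are not supported:

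- A reader might infer that the trial will test its VOCs at the wrong level. The SAP has the adjusted wording and the protocol points to 12.3, so the analysis would probably be right.
- A reader might infer that the superiority p-values should be declared outside the controlled error rate. Protocol 12.2.1 already ties the 0.025 to the inferiority nulls, and superiority is part of the stated primary and key secondary objectives. Changing its status is a design decision, not a correction.
- A reader might take the 5% overall error in the two-cohort passage of Protocol 12.3 and SAP 2.1 as a mistake. It can be read as two-sided, and that branch cannot arise with one cohort tested.

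**What to change.** In Protocol 12.7.2, replace the 97.5% CI in the VOC criterion with the adjusted CI per Section 12.3. With one tested cohort its two-sided coverage is 1 - 2 x 0.025/k: 95%, 97.5%, 98.33%, 98.75% and 99% for k=1 to 5. This brings the protocol into line with SAP 4.3.1.2. The 97.5% CI for the index virus in 12.6.2 stays.

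The cost is one phrase, with no new data or analyses. For k of 3 or more the threshold becomes stricter than the literal 12.7.2 text. For k=3, power per VOC at true ratio 1 and 450 evaluable is 0.873 instead of 0.903, under the same SD assumption. That is the price of the multiplicity rule the plan already adopts in 12.3.

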12.7.3 Sensitivity and Supportive Analyses

The same sensitivity and supportive analyses described for the primary estimand in Section 12.6.3 will also be repeated for each of the VOCs in Part A. Multiple imputation sensitivity analyses will only be performed for the Part A cohort formally tested for non-inferiority of ABNCoV2 to Comirnaty.

12.7.4 Subgroup Analyses

The same subgroup analyses described for the primary estimand in Section 12.6.4 will be performed for each of the VOCs in Part A.

12.8 Exploratory Endpoints

Geometric mean titers of neutralizing antibodies against the SARS-CoV-2 index virus and VOCs, along with their corresponding 95% CIs, will be summarized by time point and cohort for Part A to explore the kinetics of humoral responses over time. Like for the primary analysis, COVID-19 infection is an intercurrent event for analyses of later time points due to its effect on humoral responses. Subjects with evidence of infection after the 2 week peak time point therefore will be removed from the Immunogenicity Analysis Set for these exploratory kinetic analyses. That is, not only will subjects with AEs of COVID-19 and positive PCR tests be removed, but additionally, due to the longer duration between follow-up visits and the possibility of asymptomatic COVID-19 infections, nucleocapsid protein testing will be used to remove subjects who have evidence of COVID-19 infection. Results will be presented in both tabular and graphical format.

ABNCoV2-03

Edition 8.0

Total antibody titers measured by ELISA in subsets of the Part A cohorts and cellular immune responses measured by ELISpot in the immunogenicity subsets of the Part B cohorts will also be summarized using geometric means and their 95% CIs. The difference between the ABNCoV2 and Comirnaty vaccination groups in the Part A cohorts with respect to total antibody titers will also be described by the ratio of their GMTs (ABNCoV2 vs. Comirnaty) and corresponding 95% CIs within each cohort. All analyses will be considered descriptive. The GMTs and 95% CIs will also be plotted as a function of time for each assay and vaccination group for the applicable parts and cohorts on the log₁₀ scale.

Fold increases, defined as post-baseline titers divided by the baseline titers, will be summarized by assay, vaccination group (if applicable), and timepoint within each part and cohort. They will further be summarized by subgroups (age, baseline titer category, baseline comorbidity, previous vaccination regimen, history of known SARS-CoV-2 infection, and time from previous vaccination). Similar to the titers, fold increases will also be summarized by geometric means and corresponding 95% CIs.

The combined cohort analyses for Part A will be similar to the analyses performed for each cohort.

12.9 Analyses of Safety

Safety data will be summarized descriptively. Adverse event data will be coded using the Medical Dictionary for Regulatory Activities (MedDRA). Solicited and unsolicited AEs will be summarized by system organ class, preferred term, and cohort. Solicited and unsolicited AEs that meet certain criteria, e.g., \geq Grade 3, serious, related to vaccination, within 8 days after trial vaccination, or during the active trial phase, will be summarized similarly.

Based on AE and SARS-CoV-2 PCR testing results in Part A, the proportion of subjects testing positive for COVID-19 infection by timepoint, and at any time after trial vaccination, will be summarized by vaccination group for each of the cohorts. For Part B, proportions will be summarized for each cohort by timepoint and overall.

Vital signs and laboratory data will be graded according to the scales in "Toxicity Grading Scale for Healthy Adult and Adolescent Volunteers Enrolled in Preventive Vaccine Clinical Trials" (FDA, 2007) and reported by toxicity type and grade. Summaries will focus on subject level changes, thus shifts from baseline in toxicity grade or normal range indicator will be summarized by vaccination group and cohort.

ABNCoV2-03

Edition 8.0

12.10 Timing of Analyses

12.10.1 Primary Analysis

The primary analysis for the trial will occur after all subjects have completed the 2 months of follow up. All planned immunogenicity and safety analyses will be performed. A data review meeting will take place once all data are entered into the database prior to database lock. Once the trial data are clean and any queries resulting from the data review meeting are resolved, the database will be locked and unblinded for the analysis. A full CSR will be written for this analysis.

